## Pre-Intervention Evaluations

These evaluations occur prior to the subject receiving any study interventions.

# • Screening

At the screening visit, the subject will have diagnosis confirmed and medical history reviewed. Inclusion and exclusion criteria will be completed.

# • Pre-Entry

Screening and pre-entry may occur concurrently. Consent will be obtained. EKG and blood tests will be completed at the visit.

## On-Study Evaluations

Blood chemistries, liver function tests, and hematology (Comprehensive Metabolic Panel [CMP] and CBC with differential) will be performed at Month 3, Month 6 and Month 12. FXTAS Rating Scale, neuropsychological tests, Computed Dynamic Posturography, instrumented Timed up and go test, and rating scales for movement disorders will be performed four times during the study. The allowable time window is Schedule of Evaluations ±7 days.

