# Design and Outcomes

The design of this study is an open label study conducted at one center. The primary outcome is change in the FXTAS Rating Scale (FXTAS-RS). Secondary outcome measures include neuropsychological tests (Behavioral Dyscontrol Scale, Stroop, WAIS PIQ, WASI, Animal Naming, Purdue Pegboard, Digits Backwards, Symbol Digits, and COWAT), instrumented Timed up and go (iTUG) test, Computed Dynamic Posturography (CDP), Activities-specific balance confidence (ABC) scale, Beck Anxiety Inventory (BAI), and Center for Epidemiological Studies Depression Scale Revised (CESD-R).

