## Sample size and population

Sample size for the initial pilot study is ten patients. All patients will meet critieria for possible, probable, or definite FXTAS per the Jacquemont et al diagnostic criteria (Jacquemont, 2003). There will be no stratification or randomization.

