#### STUDY OBJECTIVES

# Primary Objective

The hypothesis tested is that citicoline will result in improvement of scores on the FXTAS Rating Scale after 12 months of treatment. The null hypothesis is that there will be no difference between baseline and final outcome measures on the FXTAS Rating Scale. This scale will be performed by the principal investigator, a movement disorder neurologist involved in the development of this scale.

Secondary Objectives

There are two secondary hypotheses. First, we hypothesize that subjects will have stabilization of cognitive decline on citicoline. This hypothesis will be tested by measuring scores on the following neuropsychological tests: Behavioral Dyscontrol Scale, Stroop, WAIS PIQ, WASI, Animal Naming, Purdue Pegboard, Digits Backwards, Symbol Digits, and COWAT. Second, we hypothesize that patients will improve on Computed Dynamic Posturography and the instrumented Timed up and go test. The secondary outcomes will be performed by the study team and led by the site investigator.

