# STUDY INTERVENTIONS

#### Interventions, Administration, and Duration

Ten subjects will receive 1,000mg once daily of citicoline. Each subject will stay on the study drug for 12 months. The outcome measures will be assessed at baseline and then again at the end of month 3, month 6, and month 12. The subjects will continue taking the same study drug at the same dose throughout the entire trial. There are no expected side effects, however, adverse events will be monitored throughout the study. Subjects will be seen and treated in the outpatient Movement Disorders Clinic at Rush. Subjects will come to the clinic for 6 in person visits and 3 telephone visits will be conducted. All patients may remain on other medications for neurologic signs, but the dose of these medications needs to remain stable during the 12 months of the study.

The Handling of Study Interventions

The study drug will be manufactured by Jarrow Formulas and purchased from the online retailer ProVitaminas in the form of 250mg capsules. The study drug will then be shipped to the Principal Investigator at Rush. The study drug will be dispensed by the study team at Rush who will dispense the study drug to the subjects. The study drug will be stored at room temperature in the Parkinson Disease and Movement Disorder clinic which will be secured by lock. The study drug will be provided to the subjects in pill bottles. They will receive four capsules of 250mg daily for the 12 months of intervention. Subjects should take four capsules once a day at mealtime, or two capsules twice a day at mealtime if they are having upset stomach. Subjects will be asked to return any unused study drug after 12 months to Rush. Study intervention accountability records will be completed according to the Manual of Operations.

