## Outcome and Data Analysis

- Primary outcome (Aim 1): The primary hypothesis will be tested using a paired t-test using means of the total FXTAS Rating Scale score before and after treatment. Linear regression will be used to determine if there is an association among outcome, gender, age, race, or ethnicity. This outcome will be determined by the rating of patients from a blinded movement disorders neurologist.
- Secondary outcomes (Aim 2): Secondary hypotheses will be tested using paired ttests on the neuropsychological tests, CDP, iTUG, and the ABC scale.
- Side effects (Aim 3): Adverse events will be recorded and classified as to seriousness of the side effect and likelihood the side effect is related to the study drug. For side effect analysis, frequency analysis will be done.

  Sample Size and Accrual: Sample size was estimated using published means and standard deviations of the FXTAS-RS in FXTAS subjects. To allow for attrition, 10

subjects will be recruited. Intent to treat analysis will be performed. The number of subjects lost to follow-up is likely to be low due to the relative lack of efficacy of other forms of treatment for this particular symptom of FXTAS. For the FXTAS-RS outcome, a sample size of 58 patients is needed for a 20% effect size, using a mean score of 36.6 and a standard deviation of 11 with a mean change of -7.3, based on a power of 80% and  $\alpha$ =0.5. However, the first phase of testing is a pilot study looking at study methods and safety. We will not have adequate sample size to determine efficacy, but will be able to use the pilot data to plan the larger phase III study.

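### With one treated arm and the same cognitive and balance tests given four times, a practice gain would count toward both secondary hypotheses, and the plan has no means of showing it

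*Combined protocol and SAP*

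**What the plan says.** - **Design.** Under Design and Outcomes, "The design of this study is an open label study conducted at one center". Under Sample size and population, "There will be no stratification or randomization". Under Interventions, Administration, and Duration, "Ten subjects will receive 1,000mg once daily of citicoline". There is no concurrent comparison group.
- **Repetition.** The same section states: "The outcome measures will be assessed at baseline and then again at the end of month 3, month 6, and month 12". On-Study Evaluations says that the FXTAS-RS, the neuropsychological tests, CDP and iTUG "will be performed four times during the study". Table 2 agrees.
- **Before baseline.** Table 2 places only the MMSE at screening. The Pre-Entry text adds an EKG and blood tests. No test from the battery, no CDP and no iTUG precedes baseline.
- **Hypotheses.** Under Secondary Objectives: "First, we hypothesize that subjects will have stabilization of cognitive decline on citicoline". Then: "Second, we hypothesize that patients will improve on Computed Dynamic Posturography and the instrumented Timed up and go test".
- **Analysis.** Under Outcome and Data Analysis: "Secondary hypotheses will be tested using paired ttests on the neuropsychological tests, CDP, iTUG, and the ABC scale". No visits are named for these comparisons. The Primary Objective sets baseline against final, but only for the FXTAS-RS.
- **Not mentioned anywhere.** Alternate test forms, a practice session, correction for practice, or an external comparator.

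**The concern.** Timed, fluency, dexterity and posturography tasks are performance tests, on which a second attempt may go better than the first for reasons unrelated to treatment. Baseline is the only session in the study with no earlier in-study exposure, and it is the natural reference for a paired test.

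In a controlled trial the practice gain would be present in both arms and would largely cancel. Here it stays in the estimate. Its direction matters: on cognition it would offset a real decline, which then looks like stabilization, and on CDP and iTUG it would look like improvement. Both are the results the plan hopes to see.

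The choice of test does not cure this, because an equivalence test on the same change score would carry the same shift. The pilot data are also intended for planning a phase III study, so an inflated change could carry over into that design.

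**Working it through.** **The plan's own figures.** The documents give no practice effect, retest correlation or expected cognitive decline, so there is no figure on this point to reproduce. The only computed figure, 58 patients, concerns the FXTAS-RS. It follows from a two-sample formula with one-sided α read as 0.05: n per arm = 2 × [11 × (1.645 + 0.842) / 7.3]² ≈ 28.1, so 29 per arm and 58 in total. Nothing below depends on it.

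**Inputs**
- n = 10, from the plan.
- Paired t-test, from the plan. Two-sided α = 0.05 is assumed. With 9 degrees of freedom the critical value is 2.262.
- Retest correlation r = 0.6 to 0.8, assumed.
- Practice gain g = 0.3 to 0.5 baseline SD, assumed.
- True drug effect zero in step 1.

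**Formulas.** In baseline-SD units, with equal SDs at the two visits, the SD of change is √(2(1 − r)). The standardized change is dz = g / √(2(1 − r)) and the noncentrality is λ = dz × √10. The chance of a significant result in the improvement direction is P(t′ > 2.262), where t′ is noncentral t with 9 degrees of freedom and noncentrality λ.

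**Step 1. Practice gain alone, no drug effect**

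| r | SD of change | g = 0.3 | g = 0.4 | g = 0.5 |
|---|---|---|---|---|
| 0.6 | 0.894 | 15.6% | 24.4% | 35.2% |
| 0.7 | 0.775 | 19.4% | 30.9% | 44.6% |
| 0.8 | 0.632 | 26.9% | 43.1% | 60.6% |

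For example, r = 0.8 and g = 0.3 give dz = 0.3 / 0.632 = 0.474, λ = 1.50 and 26.9%. The comparator is 2.5%, because only one tail of the two-sided test counts as improvement.

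**Step 2. Practice set against a true decline.** Take a true 12-month decline of 0.5 SD (assumed) and r = 0.8. The chance of a significant decline is:

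| Practice gain (SD) | Visible decline (SD) | Detected |
|---|---|---|
| 0 | 0.5 | 60.6% |
| 0.2 | 0.3 | 26.9% |
| 0.3 | 0.2 | 14.4% |
| 0.4 | 0.1 | 6.5% |

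With no practice gain at all, detection is 44.6% at r = 0.7 and 35.2% at r = 0.6. Ten subjects would usually miss this decline at those correlations anyway, so a non-significant paired test cannot establish stability with or without practice.

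**Step 3. Does sample size help?** Apply the same single-arm paired test to 58 subjects with r = 0.8 and g = 0.2. Then dz = 0.316, λ = 0.316 × √58 = 2.41, and significant improvement occurs in 66% of trials, against 14% at n = 10. More subjects make the artefact easier to detect and do not shrink it.

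**Step 4. The month-3 reference.** If the 0.5 SD decline is linear, nine months carry 0.5 × 9/12 = 0.375 SD. At r = 0.8, λ = 0.375 / 0.632 × √10 = 1.875, and detection is 39%. The contrast is useful as an estimate with an interval, but weak as a test.

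**The case against.** **Is there any practice effect in these patients?** The documents do not show one. Subjects scoring below 25 on the MMSE and those with dementia are excluded, which makes learning plausible. Against that, Table 1 lists short-term memory and executive deficits among the minor diagnostic signs, and the tests are three to six months apart. Some patients come from existing follow-up, and their earlier exposure to these tests is unknown. A reader might infer that the secondary results will be biased by a known amount. That is not supported. What stands is that a gain, if present, could not be told apart from a drug effect.

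**Is baseline the reference?** For the secondary outcomes this is an inference, though a fair one.

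**It is only a pilot.** The plan says it cannot determine efficacy, and this softens the point. But the reason given is sample size, which step 3 shows is not the cure. The secondary hypotheses are still tested, and the data go forward to phase III planning.

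**The single arm is the root cause.** True: placebo response is confounded in the same way. A reader might conclude that a control arm is required or that the secondary outcomes are worthless. Neither follows for a ten-subject pilot. Practice is the part of the problem that can be partly addressed within the chosen design.

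**The Manual of Operations may cover test forms.** It is cited for drug accountability and adverse-event reporting, not for test versions. If it does cover them, one sentence in the protocol settles that part.

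**Scope.** The argument fits the battery, CDP and iTUG. It fits the ABC questionnaire and the clinician-rated FXTAS-RS less well. No iTUG metric is named, so the direction that counts as improvement on that test still has to be defined.

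**Conclusion.** The point holds as a limit on interpretation that is cheap to reduce. The single arm, the four administrations, the absence of battery testing before baseline and the paired analysis are stated in the documents. The lack of parallel forms or practice correction rests on their silence, and the baseline reference for secondary outcomes is inferred.

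The size is illustrative. With n = 10, r = 0.6 to 0.8, a gain of 0.3 to 0.5 SD and no drug effect, significant improvement on a given test would occur in about 16% to 61% of trials, against 2.5% nominal. Smaller gains give smaller figures: 9% to 14% at 0.2 SD over the same correlations. It would go too far to say that the plan's secondary findings are wrong, or that practice is known to occur in this population.

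**What to change.** **Outcome and Data Analysis**
- Name the visits compared for each secondary outcome.
- For every neuropsychological test, CDP and iTUG, report the mean change with 95% CI for baseline to month 12 and for month 3 to month 12.
- State that stabilization or improvement will not be attributed to citicoline when the gain is confined to baseline to month 3.
- State that non-significance of either contrast is not evidence of stability.

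A rule that the two contrasts must merely agree would be too lenient, because two non-significant results in ten subjects would agree easily (step 4).

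**On-Study Evaluations**
- Use parallel versions in a fixed rotated order for the tests that have them, for example letter and category fluency and symbol substitution. CDP, iTUG and the rest of the battery would rely on the month-3 contrast.

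**Cost.** Some analysis wording and alternate test sheets. No new visit is needed, since the month-3 data are already planned. The month-3 contrast covers nine months, all on treatment. It misses any drug effect complete by month 3, so the attribution rule is deliberately cautious. It also still carries whatever learning occurs at later sessions. It is therefore a supporting estimate beside the full 12-month change, not a replacement for it.

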#### Baseline

The baseline (entry) visit will occur at least two weeks after the screening visit to allow for adequate study drug supply. Study drugs will be dispensed at the entry visit.

# • Intervention Discontinuation Evaluations

Evaluations done at the time of discontinuation include blood chemistry, hematology, FXTAS-RS, neuropsychological tests, Computed Dynamic Posturography, instrumented Timed up and go test, and the rating scales. In addition, an adherence assessment will also be done.

## Post-Intervention Evaluations

Neurological examinations will be performed according to the standard of care by the treating neurologist/investigator.

## • Final Evaluations

The final visit will consist of blood chemistry and hematology, neurological examination, FXTAS Rating Scale, neuropsychological tests, Computed Dynamic Posturography, instrumented Timed up and go test, rating scales, and adherence assessment.

Special Instruction and Definitions of Evaluations

The source document will include all of the following listed below.

- Informed Consent: The patient will have an opportunity to review the consent form and ask any questions prior to signing the form. If the patient has dementia, they will be excluded from the study. Documentation of the consent will be given to the subject, and copies will be maintained in the study chart and the hospital record.
- Documentation of FXTAS: Diagnosis of FXTAS will need to be documented prior to entry in the patient's chart.
- Medical History: The subject's history regarding FXTAS will be obtained or a record of this history secured for the study chart. A complete social history, family history, and review of systems will also be performed.
- Treatment History: Allergies will be reviewed. Prior and current medications and other treatments will be reviewed and documented.
- Clinical Assessments: Clinical assessment procedure will be reviewed at the baseline
  entry visit and neurological examination performed. Clinical assessments to review
  safety, tolerability, and effectiveness will be conducted at each face-to-face visit or
  over the phone. Neurological examination will occur at the face-to-face visits only.
  Change in neurological signs or symptoms, adverse events, or tolerability issues
  should be recorded on the CRFs.
- Laboratory Evaluations: Blood chemistry and hematology will be performed and the resulting laboratory result form placed in the study record.
- Questionnaires and Rating Scales: Scoring for each item on the FXTAS Rating Scale will be recorded in the scoring grid. Scoring for the neuropsychological tests, CDP, iTUG, ABC, BAI, CESDS-R, and MoCA will be recorded in the CRF.
- Adherence Assessments: Pill counts and questionnaires will be filled out at every phone or in person visit.

## Off-Intervention Requirements

Recording of adverse events for subjects after the study will occur in the setting of regular care with the treating neurologist.

## FXTAS Rating Scale

The FXTAS-RS was designed to measure the severity of motor signs of FXTAS, tremor, ataxia, and parkinsonism. The scale was developed from a combination of three separate measures: the Clinical Rating Scale for Tremor (CRST), the International Cooperative Ataxia Rating Scale (ICARS), and the Unified Parkinson's Disease Rating Scale (UPDRS). The resultant scale has 44 items and a total score of 226. The tremor sub-

domain (score range 0-53) assesses action and postural tremor, drawing, and handwriting. The ataxia sub-domain (0-73) assesses posture and gait, limb ataxia, dysarthria, and oculomotor disturbances. The parkinsonism sub-domain (0-100) assesses bradykinesia, gait and balance, rest tremor, and rigidity (Tassone, 2010). The FXTAS-RS is relatively safe and simple to administer. It uses a quantitative scale format that has strong internal consistency and good inter- and intrarater reliability with different patient populations, including geriatric patients. It has specifically been clinically validated for evaluating motor signs in FXTAS patients.

For this study, improvement will be defined as a 20% improvement on the FXTAS-RS.

# MANAGEMENT OF ADVERSE EXPERIENCES

There are no common adverse events with citicoline in adult studies. Adverse events will be documented on the adverse event form and sent to the independent medical monitor. Due to its pharmacological effects on the dopaminergic system, citicoline may enhance the effects of L-Dopa. Therefore, any subjects taking L-Dopa during the study will be monitored very closely for adverse events (EFSA, 2013).

# CRITERIA FOR INTERVENTION DISCONTINUATION

Criteria and rules for stopping subject treatment include: new toxicological findings or serious adverse events, the patient withdraws consent without need for justification, the patient is no longer able to participate for medical reasons (such as surgery), if eligibility criteria are being violated, the subject develops significant neuropsychiatric symptoms such as suicidal ideation or psychosis, or if the subject fails to comply with the protocol. Subjects who stop treatment will still be asked to complete a final visit with rating scales and blood work.

## STATISTICAL CONSIDERATIONS

#### General Design Issues

The primary and secondary outcomes will be analyzed using SPSS. The independent medical monitor will review adverse event data and the final analysis. There will be no interim analysis performed. There will be no stratification.

## Outcome and Data Analysis

- Primary outcome (Aim 1): The primary hypothesis will be tested using a paired t-test using means of the total FXTAS Rating Scale score before and after treatment. Linear regression will be used to determine if there is an association among outcome, gender, age, race, or ethnicity. This outcome will be determined by the rating of patients from a blinded movement disorders neurologist.
- Secondary outcomes (Aim 2): Secondary hypotheses will be tested using paired ttests on the neuropsychological tests, CDP, iTUG, and the ABC scale.
- Side effects (Aim 3): Adverse events will be recorded and classified as to seriousness of the side effect and likelihood the side effect is related to the study drug. For side effect analysis, frequency analysis will be done.

  Sample Size and Accrual: Sample size was estimated using published means and standard deviations of the FXTAS-RS in FXTAS subjects. To allow for attrition, 10

subjects will be recruited. Intent to treat analysis will be performed. The number of subjects lost to follow-up is likely to be low due to the relative lack of efficacy of other forms of treatment for this particular symptom of FXTAS. For the FXTAS-RS outcome, a sample size of 58 patients is needed for a 20% effect size, using a mean score of 36.6 and a standard deviation of 11 with a mean change of -7.3, based on a power of 80% and  $\alpha$ =0.5. However, the first phase of testing is a pilot study looking at study methods and safety. We will not have adequate sample size to determine efficacy, but will be able to use the pilot data to plan the larger phase III study.

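### The 58 patients stated as needed do not follow from the plan's paired t-test, at the printed alpha of 0.5 or at 0.05

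*Combined protocol and SAP*

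**What the plan says.** Under Outcome and Data Analysis, the Aim 1 entry names the primary test: "The primary hypothesis will be tested using a paired t-test using means of the total FXTAS Rating Scale score before and after treatment". The study has a single arm; the synopsis states that "There will be no stratification or randomization".

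The Sample Size and Accrual text in the same section says that "Sample size was estimated using published means and standard deviations of the FXTAS-RS in FXTAS subjects" and then that "a sample size of 58 patients is needed for a 20% effect size". Its inputs are a mean score of 36.6, an SD of 11, a mean change of -7.3, 80% power and an alpha printed as 0.5. It then presents the 10-patient study as a pilot: "We will not have adequate sample size to determine efficacy".

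The Primary Objective gives a directional hypothesis, that "citicoline will result in improvement of scores on the FXTAS Rating Scale after 12 months of treatment", beside a non-directional null: "The null hypothesis is that there will be no difference between baseline and final outcome measures on the FXTAS Rating Scale". The plan does not say whether the test is one- or two-sided, whether 11 is the SD of scores or of change, or what pre-post correlation was assumed.

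**The concern.** This is the plan's only power statement, and 0.5 is its only stated significance level. Three things do not fit together.

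- An alpha of 0.5 with these inputs should call for very few patients, not 58.
- If 0.5 is a slip for 0.05, a paired test of a change of about two thirds of an SD should still need far fewer than 58.
- The 20% label is ambiguous. It could mean a 20% fall in the mean score or a standardised effect of 0.20, and these differ by a factor of about three.

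As printed, the reader cannot tell at what level the primary test will be judged, what change 10 patients can detect, or which design and effect 58 refers to. The plan intends to use the pilot to design a phase III trial, so a mislabelled 58 could be carried into it.

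**Working it through.** **Inputs.** From Sample Size and Accrual: mean 36.6, change 7.3 (absolute value), SD 11, power 80%, alpha 0.5 as printed. An alpha of 0.05 is also tried, as an assumption. From Aim 1: paired t-test. The pre-post correlation ρ is not given, so a range is shown.

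**The effect.** 7.3/36.6 = 0.20, so the 20% matches a percentage change in the mean. The standardised effect, if 11 is the SD of change, is d = 7.3/11 = 0.664.

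**Step 1: the plan's figure with its own test, 11 as the SD of change.** The normal formula is n = ((z_α + z_power)/d)², with z_power = 0.8416. Exact values use the noncentral t distribution.

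| Alpha | Normal formula | Exact n |
|---|---|---|
| 0.5 two-sided | ((0.6745 + 0.8416)/0.664)² = 5.2 | 6 |
| 0.5 one-sided | 1.6 | 2 |
| 0.05 two-sided | ((1.960 + 0.8416)/0.664)² = 17.8 | 20 |
| 0.05 one-sided | ((1.645 + 0.8416)/0.664)² = 14.0 | 16 |

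None is 58. With 58 patients, power at two-sided 0.05 would be 99.9%, not 80%.

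**Step 2: 11 as the SD of scores.** Then SD of change = 11 × √(2(1 − ρ)).

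| ρ | SD of change | n, two-sided 0.5 | n, two-sided 0.05 | n, one-sided 0.05 | Power of 10 patients, two-sided 0.05 |
|---|---|---|---|---|---|
| 0 | 15.56 | 10 | 38 | 30 | 26% |
| 0.5 | 11.00 | 6 | 20 | 16 | 47% |
| 0.7 | 8.52 | 4 | 13 | 10 | 68% |
| 0.8 | 6.96 | 3 | 10 | 8 | 84% |

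For n = 58 to give exactly 80% power at two-sided 0.05, the SD of change must be 19.5, so ρ = 1 − 19.5²/(2 × 11²) = −0.57. That is implausible for repeated scores on one scale. At one-sided 0.05 the SD of change must be 22.1, which puts ρ below −1 and is impossible.

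**Step 3: the printed alpha against the pilot statement.** At two-sided 0.5, 10 patients have 92% power if the SD of change is 11, and 80.1% even at ρ = 0. The paragraph says that 10 are not enough, so 0.5 cannot be the intended value. At two-sided 0.05, 10 patients reach 80% only if the SD of change is 7.33 or less, that is, ρ of about 0.78 or more.

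**Step 4: what does return 58.**

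- *Two independent groups*, change 7.3, SD 11, one-sided 0.05: 2 × (11 × (1.645 + 0.8416)/7.3)² = 28.08, so 29 per group and 58 in total (exact t also gives 29, power 80.3%). At two-sided 0.05, exact t gives 37 per group, 74 in total.
- *One-sample test with standardised effect 0.20*, two-sided 0.5: (0.6745 + 0.8416)²/0.20² = 57.5, so 58. Exact t gives 58 counting the favourable tail only and 54 counting both. At two-sided 0.05 the normal formula gives 196.2, so 197, and exact t gives 199.

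The first is not this single-arm design. The second ignores the stated change, since 0.20 × 11 = 2.2 points, not 7.3; an effect of 0.20 with a change of 7.3 would need an SD of change of 7.3/0.20 = 36.5.

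**Step 5: dropout.** The plan gives no rate and expects loss to be low. Going from 20 to 58 would need 1 − 20/58 = 66% loss.

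**The case against.** The strongest reply is that 58 may never have been meant for this trial's paired test. The test is named under Aim 1, while 58 stands in separate text that goes on to call this study a pilot and to mention a larger phase III trial. Read as the total for a future two-arm comparison at one-sided 0.05, 58 is correct arithmetic with a missing label. Replacing it with 20 would then insert a wrong number. This stands as a possibility, and it governs the order of the remedy: the sponsor must first say which design 58 refers to. It does not rescue the paragraph, because no two-arm design is described anywhere, the paired test is the only primary test in the plan, and alpha is still printed as 0.5.

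A second reply is that 58 does follow at the printed alpha if the 20% is a standardised effect. That discards the stated -7.3 and 11. It also conflicts with the FXTAS Rating Scale section, which defines improvement as a percentage of the scale.

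Third, 0.5 is almost certainly a slip for 0.05, and few readers would apply it. That is fair, but changing that one figure still leaves 58 unsupported.

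Fourth, the practical weight is limited: enrolment is fixed at 10, and the plan disclaims efficacy power. This stands in full.

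**Conclusion.** The concern holds. With the stated change and SD, no paired t-test gives 58 at alpha 0.5 or 0.05, one- or two-sided, unless the pre-post correlation is about −0.57 (two-sided 0.05). Against the stated 58, the two-sided paired test needs 6 patients at 0.5 and 20 at 0.05 if 11 is the SD of change. If 11 is the SD of scores, it needs at most 10 and at most 38 respectively for any non-negative correlation.

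The printed alpha contradicts the paragraph's own statement about 10 patients; that result needs only a two-sided reading and a non-negative correlation (a one-sided reading needs fewer still). The 0.05 figures rest on the assumption that 0.05 was intended. Two incompatible calculations return 58, and the documents do not show which, if either, was used.

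This should be fixed because it is the plan's only significance level and only sample size calculation. It affects the correctness of the stated plan and the planning of the later trial, not the size of this one.

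**What to change.** Rewrite the sample size paragraph, in this order:

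1. Say which design, test and effect 58 refers to. If it was meant for a future two-arm trial, label it as a two-arm total with its sidedness (58 at one-sided 0.05, 74 at two-sided 0.05). Otherwise remove it.
2. Correct alpha and state sidedness. Two-sided 0.05 is the presumption, since it matches the no-difference null in the Primary Objective; the sponsor must confirm it.
3. State, from the published source, whether 11 is the SD of scores or of change.
4. Give the paired-test figures conditionally, for example: *Paired t-test, two-sided alpha 0.05, 80% power, mean change -7.3: 20 patients if the SD of change is 11; if 11 is the SD of scores, 38, 20, 13 or 10 patients at pre-post correlation 0, 0.5, 0.7 or 0.8. With 10 patients, power is 47% if the SD of change is 11 (26% to 84% for correlation 0 to 0.8).* If a one-sided test is chosen, the corresponding sizes are 16, and 30, 16, 10 or 8.
5. Replace the 20% effect size label with a 20% mean change (standardised effect 0.66 if the SD of change is 11).

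Enrolment stays at 10 as a pilot. The cost is the wording of one paragraph and a check of one published SD.
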